#### ***5.3.1 Screening Period (Visit -1, Day -28 to Day -4)***

During the screening period, subjects will be seen in the clinic and the study will be described to them. Parents/legal guardian/caregiver will be asked to sign the informed consent and each subject to provide written or verbal assent. After obtaining informed consent, subjects will be screened for participation in the study. Screening procedures may be performed within 4 weeks prior to the start of the dose optimization period of the study. Procedures to be performed at Screening:

1. Obtain a signed consent and verbal or written assent. No screening procedures may be initiated prior to obtaining parent/legal guardian/caregiver signature on the informed consent form and subject's assent.
2. Confirm inclusion/exclusion criteria.
3. Assign subject number, sequentially.
4. Document medical history.
5. Perform a physical examination, including vital signs (sitting BP, HR, RR, oral body temperature), body weight, and height;
6. Calculate BMI
7. Collect blood and urine for clinical laboratory assessments

Amendment 4: Version 5.0 May-08-2013

Amendment 3: Version 4.0 December-11-2012

Amendment 2: Version 3.0 October-31-2012

Amendment 1: Version 2.0 August-02-2012

Final Protocol May-25-2012

- Complete Blood Count (including differential and platelet count)
- Blood Chemistry
- Urine drug screen (for drugs of abuse) and cotinine (for nicotine).
- Urine pregnancy test on all females of child-bearing potential.

8. Perform a 12-lead electrocardiogram (ECG).
9. Obtain ADHD-RS-IV score.
10. Perform the Mini-kid 6.0
11. Perform the Weschler Abbreviated Intelligence Test.
12. Perform one level finding math test and one PERMP at demonstrated level.
13. Record all medications taken within 30 days prior to Screening.
14. Record adverse events.

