### ***5.3.2 Washout Period (Day -3 to Day -1)***

After receipt of all the test results and confirmation that a subject is eligible to participate in the study, eligible subjects who are currently taking any medication for ADHD will begin a washout period of three days prior to the Baseline visit (Day 0).

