Age will be calculated as (date of informed consent – date of birth + 1) / 365.25.

Baseline

Baseline is defined as data collected at Visit 0 (Day 0). If data was not collected at Visit 0, the last data available prior to Visit 0 will be used as the baseline data. However during the double

blind crossover phase change from baseline analyses will be performed taking the pre-dose data at the same classroom visit to be the baseline.

Body Mass Index

Body Mass Index (BMI) will be calculated as weight in kg / (screening height in m)².

Prior and Concomitant Medications

Prior medications are defined as those taken prior to the date of first dose of study medication. Concomitant medications are defined as those on or after the date of first dose of study medication through and including the day of the safety follow-up visit. Medications with a missing or incomplete start date will be assumed to be concomitant.

Concomitant medications will be assigned to either the Dose-Optimization Period or the double-blind Treatment Period of the study according to the start date, and will be summarized separately. Concomitant medications for which a missing or incomplete start date makes it impossible to determine which period of the study they started in will be counted as starting in the Dose-Optimization Period.

Treatment-emergent adverse event

A treatment-emergent adverse event (TEAE) is one which first occurs or worsens in severity after the first patch application and not later than 30 days following last patch removal. Adverse events are collected through the last study visit. Those AEs with a start date equal to the date of first patch application will be considered as TEAEs.

Adverse events for which a missing or incomplete start date makes it impossible to determine whether or not they were treatment-emergent will be counted as being treatment-emergent.

Adverse events will be assigned to either the Dose-Optimization Period or the double-blind Treatment Period of the study according to the start date, and will be summarized separately. Adverse events for which a missing or incomplete start date makes it impossible to determine which period of the study it started in will be counted as starting in the Dose-Optimization Period

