7.4.2 Concomitant Medications

All prior and concomitant medications recorded in the electronic case report form (eCRF) will be coded to generic term and all matching Anatomic Therapeutic Classification (ATC) codes using the current version of WHO Drug. Summaries will be prepared using the coded generic term.

The number and percentage of subjects who had prior medications will be provided by preferred drug name for the SP population. The numbers and percentages of subjects who had concomitant medications during the Dose-Optimization Period and during the double-blind Treatment Period will be presented separately for the SP population.

All prior and concomitant medications recorded in the eCRF will be listed.

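### The SAP calls every medication with an incomplete start date concomitant, even when a recorded stop date shows that it ended before the first patch

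*SAP*

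**What the plan says.** SAP section 5 sets out the two classes by timing. For prior use: "Prior medications are defined as those taken prior to the date of first dose of study medication". For concomitant use: "Concomitant medications are defined as those on or after the date of first dose of study medication", running through the day of the safety follow-up visit. It then adds a rule for imperfect dates: "Medications with a missing or incomplete start date will be assumed to be concomitant".

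The next paragraph assigns concomitant drugs to a study period by start date. Its default covers "Concomitant medications for which a missing or incomplete start date makes it impossible to determine which period of the study they started in"; these count as starting in the Dose-Optimization Period.

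SAP section 7.4.2 gives the tables. On prior use: "The number and percentage of subjects who had prior medications will be provided by preferred drug name for the SP population". Concomitant use is tabulated separately for each study period, also in the Safety population. Neither that section nor Protocol section 8.4.4 contains a rule on stop dates.

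The Protocol shows where the relevant records come from. Section 5.3.1 instructs sites: "Record all medications taken within 30 days prior to Screening". Section 5.3.2 adds that "eligible subjects who are currently taking any medication for ADHD will begin a washout period of three days" before Day 0. Section 5.3.3 has the first patch applied on the day after Day 0.

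**The concern.** Whether a drug overlapped with d-ATS depends on when it ended, and the rule for imperfect dates never asks. A child whose previous stimulant has no complete start date, but has a recorded stop in the washout, is labelled as using it together with study drug. The database itself shows otherwise.

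The design can produce such records. Exclusion criterion 4 bars current ADHD medication only where it controls symptoms without residual impairment and is well tolerated and adhered to. Children on less satisfactory treatment can therefore enrol, and their drug is washed out before the first patch.

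The stake is the accuracy of a safety summary. SAP section 4.2.6 lists concomitant medications among the safety assessments, and Protocol section 7.4.3 prohibits other stimulants throughout the study. An entry that shows a second stimulant alongside d-ATS, when the child had already stopped it, misstates co-exposure in a paediatric trial.

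**Working it through.** No arithmetic in the plan bears on this point. The check is to apply the SAP section 5 text to each pattern of dates, with the washout on Day -3 to Day -1 and the first patch on Day 1.

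| Case | Start date | Stop date | Overlap with d-ATS | Label under SAP 5 | Period under SAP 5 |
|---|---|---|---|---|---|
| 1 | Complete, before first dose | Before first dose | No | Prior | Not needed |
| 2 | Year only, clearly before the study (say 2010) | In the washout | No | Concomitant | None stated |
| 3 | Wholly missing | Before first dose | No | Concomitant | Dose-Optimization by default |
| 4 | Partial, could overlap the study (say enrolment year only) | Before first dose | No | Concomitant | Dose-Optimization by default |
| 5 | Wholly missing, or partial and could overlap the study | Missing or ongoing | Possible or certain | Concomitant | Dose-Optimization by default, unless the known part settles it |
| 6 | Complete, before first dose | Ongoing | Yes | Concomitant (and prior) | None stated |

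Case 1 is right. Case 5 is a sensible cautious default, because the available dates do not exclude overlap.

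Cases 2, 3 and 4 are wrong. The stop date settles the matter, and the label contradicts the definition given just before the rule. In cases 3 and 4 the period default, which also looks only at the start date, carries the wrong label into the open-label table. In case 2 it does not: the known year shows that the drug started in neither study period, so the condition for the default is not met and the text assigns no period.

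Case 6 exposes a second gap. A drug that truly continued into the study is concomitant, but its start lies before both periods, so assignment by start date leaves it without a table.

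The adverse-event rule in the same section is a useful comparison. Its default is limited to "Adverse events for which a missing or incomplete start date makes it impossible to determine whether or not they were treatment-emergent". The period default for medications has a similar limit. Only the rule that decides prior against concomitant status has none.

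**The case against.** The best defence is that counting doubtful records as concomitant is cautious for safety, that all recorded medications are listed in any case, and that SAP section 7.7 plans no inferential statistics on safety. Some material is also not visible: the case report form and most SAP appendices are not in the supplied text, so a date convention elsewhere cannot be excluded. This stands as a limit on the size of the point. It does not remove it: caution is a reason to include records whose status is unknown, not records whose stop date rules out overlap, and section 5 refers to no further convention.

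Four stronger readings are tempting, and the documents do not support them.

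- **All washed-out drugs with only a start year will appear in the Dose-Optimization table.** This is not shown where the known year is clearly before the study (case 2).
- **The prior-medication table loses these children.** The two classes are not stated to be exclusive. A washed-out drug still meets the definition of prior use and may appear in that table as well.
- **False prohibited-drug violations follow, or the Completers set shrinks.** SAP section 7.3 has major deviations reviewed on blinded data and does not say that they are derived from this label. The Completers criterion in SAP section 6.2 concerns prohibited drugs in the double-blind period, whereas the default points to the earlier one.
- **A percentage of the 90 randomised children can be quoted.** This would need the share on an ADHD drug at screening, the share of those records with an incomplete start date, and the share with a usable stop date. The documents give none of these. The 90 is also the wrong base, because the tables use the Safety population, which includes children treated in titration and never randomised.

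**Conclusion.** The point holds as a defect in a stated rule. Read literally, SAP section 5 gives a wrong label to any medication with an incomplete or missing start date and a recorded stop before the first dose. Where the start date is wholly missing or could overlap the study, it also gives a wrong entry in the Dose-Optimization medication table.

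The consequence is limited to descriptive medication summaries in the Safety population. The primary and secondary efficacy analyses do not use this label.

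The number of records affected is unknown and could be none. The conclusion assumes that some enrolled children have incomplete start dates together with recorded stop dates, and that no date convention outside the supplied text overrides section 5. That long-standing ADHD drugs are especially likely to lack a full start date is a plausible inference, not something the documents state.

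**What to change.** Replace the sentence on missing or incomplete start dates in SAP section 5 with:

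*A medication with a stop date before the first dose is prior only, whatever its start date. A medication whose known start information precedes the first dose is prior, and is also concomitant if it is ongoing or stopped on or after the first dose. A medication is assumed concomitant only when its start and stop information, taken together, leave its status undetermined.*

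Add to the paragraph on study periods:

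*A concomitant medication that started before the first dose and continued is counted in the Dose-Optimization Period.*

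Under this text, cases 2 to 4 become prior only, case 5 remains concomitant, and case 6 gains a period. An incomplete stop date that leaves the question open falls under the third sentence, so the cautious default is kept where it is needed.

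The cost is a few sentences in the SAP and a few lines of code, using dates already collected. SAP section 1 provides for a final version (SAP2) before database lock, which can carry the change.

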### ***7.4.2 Ongoing, Prior and Concomitant Therapies***

Rules for ongoing prior and concomitant therapies are as follows:

- Prescription medication for stable medical, non-psychiatric illness will be permitted during the study provided the dose has remained stable for 30 days prior to screening.
- Use of an investigational study medication within 30 days prior to screening is not permitted

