### ***7.4.3 Prohibited Concomitant Medication***

Subjects will not be allowed to take the following medications and therapies during the entire duration of the study:

- Any stimulant other than study drug (e.g. methylphenidate, amphetamine, Ritalin, Ritalin SR, Metadate ER, Concerta, dextromethylphenidate, Focalin, dextroamphetamine, Dexedrine, Adderall)
- Atomoxetine (Strattera), SSRIs and SNRIs

Amendment 4: Version 5.0 May-08-2013

Amendment 3: Version 4.0 December-11-2012

Amendment 2: Version 3.0 October-31-2012

Amendment 1: Version 2.0 August-02-2012

Final Protocol May-25-2012

- Tricyclic antidepressants
- Clonidine, MAOIs
- Mood Stabilizers (e.g. lithium, valproate, quetiapine)
- Antipsychotics (e.g. risperidone, olanzapine)
- Anticonvulsants
- Sedative hypnotics (unless stable dose at least 30 days prior to screening and during the clinical study)
- Coumarin anticoagulants
- Halogenated anesthetics
- Phenylbutazone
- Alternative therapies to treat ADHD
- Other investigational drugs

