6.2 COMPLETERS

The completers population includes all consented and randomized subjects who

- received full prescribed dose of the double-blind study medication at both test laboratory classroom sessions
- completed the full classroom tests on both test classroom sessions
- did not miss more than four consecutive days of therapy during the double blind treatment period

- did not use prohibited concomitant medications during the double blind treatment period

The Completers population will be used for supportive analyses of efficacy endpoints.

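### Filing concomitant medications by start date alone makes the double-blind table a count of new starts, so ongoing drugs taken in Weeks 6 and 7 are left out

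*SAP*

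**What the plan says.** SAP section 5 first defines the term by timing relative to treatment, with the window closing at the follow-up contact: "Concomitant medications are defined as those on or after the date of first dose of study medication through and including the day of the safety" […]. It then sorts the drugs into periods: "Concomitant medications will be assigned to either the Dose-Optimization Period or the double-blind Treatment Period of the study according to the start date". A default covers poor dates: "Concomitant medications for which a missing or incomplete start date makes it impossible to determine which period of the study they started in" are treated as having started in Dose-Optimization. No sentence carries an ongoing drug forward into the next period.

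SAP 7.4.2 plans the output for the safety population: "The numbers and percentages of subjects who had concomitant medications during the Dose-Optimization Period and during the double-blind Treatment Period will be presented separately". It also plans a table of prior medications and a listing of every recorded medication. The general rule in SAP section 7 is that double-blind summaries are shown by treatment, d-ATS and placebo, with each child contributing to both columns.

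The protocol permits some background drugs. Section 7.4.2 allows prescriptions for stable non-psychiatric illness "provided the dose has remained stable for 30 days prior to screening". Section 7.4.3 puts sedative hypnotics on the prohibited list with an exception: "Sedative hypnotics (unless stable dose at least 30 days prior to screening and during the clinical study". Protocol 7.4.1 describes concomitant therapy by use during the study and has no start-date rule.

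**The concern.** The rule in section 5 and the table in 7.4.2 measure different things. The table is worded as use during a period; the rule supplies starts within a period. For drugs taken over weeks, the two differ most for the drugs the protocol expressly allows to continue.

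SAP section 5 uses the same start-date wording for adverse events. It fits there, because the onset of an event is what is being attributed to a period. It does not fit an exposure that persists after it begins.

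Safety is a primary objective, and concomitant medication is one of the listed safety assessments. A reader who turns to the double-blind table to see what children were taking on Days 36 to 49 would find no stable sedative use even if some children took a sedative throughout. If the table is split by treatment, a drug spanning both weeks could also look like use under one treatment only, which is a false imbalance.

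**Working it through.** The plan states no figure on this point, so there is nothing to reproduce. The check sets the rule against the study calendar.

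**Inputs**
- Screening: Day -28 to Day -4 (Protocol 5.3.1).
- Dose-Optimization: Days 1 to 35; double-blind: Days 36 to 49 (SAP section 3). Week 6 is Days 36 to 42 and Week 7 is Days 43 to 49.
- Permitted background drugs and sedatives: stable for at least 30 days before screening (Protocol 7.4.2 and 7.4.3).
- Period rule: start date only; unknown starts go to Dose-Optimization (SAP section 5).

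**Step 1: latest possible start of a permitted stable drug.** With screening as late as Day -4, the start is no later than -4 - 30 = Day -34. The gap to the first double-blind day is 36 - (-34) = 70 days. No such drug can be filed under double-blind. Its start also precedes Day 1, so read literally it falls in neither period. If the either/or wording forces a choice, it goes to Dose-Optimization. Both readings leave it out of the double-blind table. This assumes one record per drug; a later change entered as a new record would carry a later start date.

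**Step 2: the rule applied to typical cases, compared with counting by overlap.**

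| Case | Taken on Days 36–49? | Start-date rule | Overlap rule |
|---|---|---|---|
| Permitted sedative, started by Day -34, taken throughout | Yes | Neither period, or Dose-Optimization | Both periods, both treatment weeks |
| Started Day 20, taken through Day 49 | Yes | Dose-Optimization only | Both periods, both treatment weeks |
| Started Day 20, stopped Day 30 | No | Dose-Optimization only | Dose-Optimization only |
| Start unknown, taken through Day 49 | Yes | Dose-Optimization only | Both periods, both treatment weeks |
| Started Day 38, taken through Day 49 | Yes | Double-blind; possibly one treatment only | Double-blind, both treatment weeks |

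The third case is handled correctly as the plan stands. The first, second and fourth are missing from the double-blind table although the drug was in use. The fifth is in the table, but no sentence says how it is allocated between d-ATS and placebo. If the start date decides, the drug is credited only to the treatment given in Week 6.

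**Step 3: is it corrected elsewhere?** SAP 7.4.2 repeats the split by period without a rule for ongoing drugs. SAP section 7 provides the split by treatment but no allocation rule. Protocol 8.4.4 has no period rule at all. Nothing changes the result of step 2.

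**The case against.** The best defence is that this is one descriptive table and little depends on it. Most of that stands. Every medication is listed, so no data are lost. Background drugs taken before first dose also appear in the prior-medication table. No efficacy model uses the concomitant-medication table. In a crossover, a stable drug taken in both weeks is present under d-ATS and placebo alike and cannot by itself create a treatment difference. None of this makes the table match its description: the prior table does not show whether use continued, and a listing does not correct a wrong percentage.

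Three stronger readings are tempting, and the documents do not support them.

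- A reader might infer that children still taking a prohibited drug in Weeks 6 and 7 slip into the Completers population because the drug began in open label. SAP 6.2 is worded by use: such a child must be one who "did not use prohibited concomitant medications during the double blind treatment period", whatever the start date. SAP 7.3 also has non-permitted medications reviewed as major violations on blinded data. Nothing says that the period flag feeds either step.
- A reader might infer that double-blind use is never split between d-ATS and placebo weeks. SAP section 7 says double-blind summaries are by treatment. Only the allocation rule for a drug spanning both weeks is missing.
- A reader might take the calendar share, 35/49 = 71%, as the fraction of on-study starts that are misfiled. It assumes uniform starts, which the documents do not give, and it includes drugs started and stopped before Day 36, which are rightly absent from the double-blind table. It is not an error rate.

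**Conclusion.** The point holds as a conflict between a stated rule and the table it feeds. As written, the double-blind concomitant-medication table would count new starts from Day 36 on while being described as use during the period. Permitted drugs whose record begins before Day 1 are excluded by construction. Drugs begun in open label are wrongly absent only if they continued past Day 35. Drugs with an undeterminable start are wrongly absent if they were taken in Weeks 6 or 7.

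The number of children affected cannot be stated, because the documents give no medication counts. No efficacy estimate, p-value or analysis population changes. The conclusion assumes that the section 5 rule is programmed as written and that each continuing drug is one record. It is worth correcting before database lock because a planned safety summary would otherwise be wrong as labelled.

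**What to change.** In SAP section 5, replace the start-date rule for medications with an overlap rule:

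- Count a medication in every period that its start-to-stop interval (or ongoing use) overlaps, including drugs started before Day 1 and still in use.
- Within the double-blind period, count it under every treatment week it overlaps, so that a drug spanning Weeks 6 and 7 appears under both d-ATS and placebo.
- Where the start date is missing, assume use in each period up to the stop date.
- Footnote the tables in SAP 7.4.2 to say that a child can appear in more than one column.

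The start-date rule for adverse events can stay. The cost is SAP wording, one derived variable and a footnote. No new data are needed, provided the eCRF records a stop date or ongoing status for each medication; the eCRF is not among the documents, so this is an assumption. The change fits in the final SAP version that SAP section 1 already schedules before database lock.

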### **6.19 Anticipated Adverse Events**

Some of the adverse events noted in more than one clinical trial of oral forms of d/l-amphetamine are: headache, decreased appetite, stomach ache, trouble sleeping, nervousness, mood swings, weight loss, dizziness, dry mouth, blurred vision, seizures (mainly in patients with a history of seizures), and slowing of growth in children. It should be assumed that the adverse event profile for the d-ATS should be similar to that found in clinical trials of oral d/l-amphetamine.

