#### ***8.4.1 Adverse Events***

All Treatment Emergent Adverse Events (TEAEs) will be classified by system organ class (SOC) and preferred term using the latest version of MedDRA dictionary. All TEAEs that occur after randomization up to 30 days after last dose of study drug will be summarized. Subjects may have more than one TEAE per system organ class or preferred term.

Unless otherwise specified, at each level of subject summarization in reporting the incidence of the AE, a subject will be counted once if the subject reported one or more events. AEs, TEAEs, SAEs, treatment-related SAEs, and TEAEs leading to premature discontinuation of study drug will be summarized by MedDRA SOC, preferred term, and stratified by intensity.

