7.7.1 Adverse Events

Treatment-emergent adverse events will be assigned to either the open-label Dose-Optimization Period or the double-blind Treatment Period. TEAEs occurring in the safety follow up after the double blind Treatment Period will be reported under the double blind Treatment Period for the last treatment they received. TEAEs for which a missing or incomplete start and/or stop date makes it impossible to determine which period of the study they started in will be counted as starting in the Dose-Optimization Period. The subject's dose of study drug at the onset of the event will be determined for all TEAEs. If a missing or incomplete start date makes it impossible to determine the dose at onset, then the dose at onset will be set to the lowest dose in the study (i.e., 5 mg/ 4.76 cm²). Adverse events that start before the first patch application will be summarized separately. For summaries, TEAEs with missing severity are assumed to be severe, and TEAEs with missing relationship to study drug are assumed to be related.

Summary statistics for TEAEs will be presented separately for the SP population on all subjects combined during the Dose-Optimization Period and by treatment arm during the double-blind Treatment Period. All summaries of adverse events will consist of the number of events and the numbers and percentages of subjects who had the events being summarized.

All TEAEs will be classified by SOC and PT using the latest version of MedDRA dictionary. All TEAEs that occur after first patch application up to 30 days following last patch application will be summarized. Subjects may have more than one TEAE per SOC or PT. Unless otherwise specified, at each level of subject summarization in reporting the incidence of the AE, a subject will be counted once if the subject reported one or more events.

The following summaries will be presented separately for the Dose-Optimization Period and the double-blind Treatment Period by the dose being taken at the onset of the events and by MedDRA SOC, and preferred term:

- Overall summary of TEAEs
- TEAEs
- Treatment-related TEAEs
- TEAEs leading to premature discontinuation of study drug
- TEAEs by intensity.

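### Adverse events that begin in the d-ATS run-in and continue unchanged stay out of the placebo-controlled table, which can understate the d-ATS versus placebo difference

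*SAP*

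**What the plan says.** SAP section 5 (Definitions) fixes the counting rule: "Adverse events will be assigned to either the Dose-Optimization Period or the double-blind Treatment Period of the study according to the start date", with the two periods summarised separately. SAP 7.7.1 repeats it: "Treatment-emergent adverse events will be assigned to either the open-label Dose-Optimization Period or the double-blind Treatment Period". It adds that "The subject's dose of study drug at the onset of the event will be determined for all TEAEs".

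Treatment-emergent status is anchored to the first patch: an event qualifies if it "is one which first occurs or worsens in severity after the first patch application and not later than 30 days following last patch removal". The first patch is open-label d-ATS, so there is no second baseline at randomisation. Events whose start date is too incomplete to place go to the Dose-Optimization Period by default (SAP 5 and 7.7.1).

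The tables are presented "on all subjects combined during the Dose-Optimization Period and by treatment arm during the double-blind Treatment Period". Protocol 8.4.1 describes the summary as "All TEAEs that occur after randomization up to 30 days after last dose of study drug will be summarized". Neither document plans a table of events ongoing at randomisation, or of events present by treatment.

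Safety is one of the two primary objectives (Protocol 4, SAP 2). The dose in use at the Week 5 visit is the dose carried into the double-blind weeks, and children who cannot tolerate d-ATS are discontinued before that (Protocol 5.1, SAP 3). Protocol 6.19 expects events such as "headache, decreased appetite, stomach ache, trouble sleeping, nervousness, mood swings, weight loss".

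**The concern.** The two crossover weeks hold the only placebo-controlled safety data in the trial, and they follow five weeks on the same drug. Several of the anticipated events could plausibly begin during titration. If one does, is tolerated and continues, it is counted once, against the run-in. It does not appear in the d-ATS column of the double-blind table. If it clears in the placebo week, that contrast is not tabulated either.

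The other by-arm safety summaries do not fill the gap for these events. Vital signs, ECG, C-SSRS and dermal data are summarised by arm in the double-blind period whatever an event's start date, but they do not measure appetite, sleep or headache. Weight is listed for Day 49 only during those weeks (Protocol 5.3.5.3) and is not among the vital-sign parameters in SAP 7.7.4. A reader comparing the two columns could therefore see a known drug effect as less different from placebo than it was.

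**Working it through.** No figure in the plan depends on this rule, so there is none to reproduce. The check is a small expected-count model; every rate in it is an assumption.

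**Inputs from the documents.** Two sequences in a 1:1 ratio (SAP 3.2); one week per treatment, Week 6 then Week 7 (SAP 3); assignment by start date (SAP 5).

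**Assumed inputs.**
- q: share of children with a tolerated event ongoing at Day 36
- s: probability that it persists through a d-ATS week
- p: probability that it resolves in a placebo week
- r: probability that a resolved event recurs on d-ATS in Week 7
- New-onset risk is the same on both treatments, so it cancels from every difference.

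**Contribution of the ongoing events, by sequence.**

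| Sequence and week | Start-date count | Present at end of week |
|---|---|---|
| d-ATS first, Week 6 (d-ATS) | 0 | q·s |
| d-ATS first, Week 7 (placebo) | 0 | q·s·(1−p) |
| Placebo first, Week 6 (placebo) | 0 | q·(1−p) |
| Placebo first, Week 7 (d-ATS) | q·p·r | q·[(1−p)·s + p·r] |

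Averaging the two sequences gives the d-ATS minus placebo differences:

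- start-date: ½·q·p·r
- end of week: ½·q·[s − (1−p) + p·r]
- shortfall (second minus first): ½·q·[s − (1−p)]

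The shortfall is half the ongoing share, multiplied by persistence on d-ATS minus persistence on placebo. It does not depend on r.

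**q = 15%, fully drug-dependent event (s = 1, p = 1).**

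- All recur in Week 7 (r = 1): start-date ½ × 15 × 1 = 7.5 points; end of week ½ × 15 × (1 + 1) = 15 points.
- None recur (r = 0): start-date 0; end of week ½ × 15 × 1 = 7.5 points.

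**Partial case (s = 0.8, p = 0.8, r = 0.5).** For q = 10, 20 and 30%, start-date gives 2, 4 and 6 points against 5, 10 and 15 at end of week.

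**Equal resolution (s = 0.5, p = 0.5, r = 0).** Both differences are 0.

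**Range for q.** Take q as run-in incidence × persistence to Day 36. Incidence of 20–40% and persistence of 50–70% give 0.20 × 0.50 = 10% up to 0.40 × 0.70 = 28%. For a fully drug-dependent event the shortfall is then ½ × 10 = 5 up to ½ × 28 = 14 points.

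**Counting any event present at any time in the week.** Here a run-in event still ongoing on the first day of a placebo week is charged to placebo. The difference becomes ½·q·[(1−p) + p·r − s]. For the fully drug-dependent event at q = 15% this is 0 with recurrence and −7.5 points without, so this count erases or reverses the contrast.

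**The case against.** The strongest reply is that nothing is concealed. Run-in events are tabulated by dose at onset, system organ class and preferred term in a period when everyone is on d-ATS, and all data are listed. Safety is descriptive, with no inferential statistics (SAP 7.7), so no planned test is biased. Selecting children who tolerate the drug is a stated design feature and not a product of the counting rule. All of this stands. It does not answer the main point: the run-in table has no comparator, and readers will compare the double-blind columns with or without a test.

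Two stronger readings are tempting, and the documents do not support them.

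- A reader might infer that the rule necessarily understates d-ATS harm. It drops ongoing events from both columns, because half the children enter a placebo week first. The difference shrinks only if events persist more on d-ATS than on placebo. That is plausible for drug effects, but neither document gives a rate.
- A reader might infer that a recurrence in the double-blind weeks is excluded because it is no longer a first occurrence. The anchor is the first run-in patch: "A treatment-emergent adverse event (TEAE) is one which first occurs or worsens in severity after the first patch application". An event that first appeared in the run-in already meets this. SAP 7.7.1 also counts numbers of events and allows several per preferred term. A recurrence therefore has its own start date and falls in the double-blind period. It follows that a 15-point contrast in both sequences cannot be displayed as nearly nothing, since the Week 7 recurrences it requires would themselves be counted.

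Worsening is unresolved. It counts toward treatment-emergent status, but neither document says whether a run-in event that worsens after randomisation gets a new start date.

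**Conclusion.** The concern holds in conditional form. On the text, a run-in event that continues unchanged cannot enter the double-blind table by arm, and no other by-arm table covers appetite, sleep or headache. The understatement equals half the ongoing share times the excess persistence on d-ATS over placebo. Under the assumed rates it runs from zero (equal resolution) to 5–14 points (full drug dependence, 10–28% ongoing). These figures illustrate the mechanism and do not estimate what this trial would show. They assume equal new-onset risk on both treatments, and that recurrences are recorded with a new start date. The change is worth making because the rule sets aside placebo-controlled information that the trial already collects. It does not put the primary efficacy analysis or any planned test in doubt.

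**What to change.** In SAP 5 and 7.7.1, before SAP2 is approved:

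1. Keep the start-date table, labelled as new events in children who had tolerated the d-ATS run-in.
2. Add a descriptive table by treatment and sequence. For each double-blind week, give the number and percentage of children with each event ongoing at the start of the week, the number resolved during it, and the number present at its end.
3. Do not use presence at any time in the week, since that charges residual d-ATS events to placebo.
4. State that a recurrence after resolution, or a worsening after randomisation, is counted under the treatment received when it occurs, and that a worsening is recorded with its own date.

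Onset and resolution dates and times are already collected (Protocol 6.17.1). The cost is one or two extra descriptive tables, and the d-ATS column will show higher percentages than the onset table alone.
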